## 12.2 Examples of Prohibited Medications

Approval Date: 15-May-2020 16:33:54 (GMT)

Approval Date: 15-May-2020 16:33:54 (GMT)

Approval Date: 15-May-2020 16:33:54 (GMT)

### **12.3.2 Criteria for Determining Inadequate Response to a Prior Migraine Preventive Medication**

Failure of a migraine-preventive medication can be assessed on the basis of efficacy or tolerability and is based on investigator judgment. The criteria below should be used to determine eligibility related to the number of prior failed migraine-preventive medications with unique mechanisms of action.

For efficacy:

- Failure is defined as a < 50% reduction in migraine days per month per investigator judgment and participant interview.
- Medications must have been started within the past 7 years.

For tolerability:

- Failure is defined as discontinuation of a drug treatment due to adverse effects.
- In assessing failure of a migraine preventive drug on the basis of inadequate tolerability, the entire medical history can be considered. For example, a participant who tried and discontinued topiramate 10 years ago for cognitive clouding should be considered to have failed this treatment.

## 12.4 Glossary of Abbreviations

Term/ Abbreviation	Definition
ACE	angiotensin-converting enzyme
AE	adverse event
AIM-D	Activity Impairment in Migraine – Diary
ALT	alanine aminotransferase
ARB	angiotensin receptor blocker
ASC-12	Allodynia Symptom Checklist
AST	aspartate aminotransferase
AUC 0-Tau	area under the concentration-time curve over the dosing interval
BID	twice-daily
BP	blood pressure
CBD	cannabidiol
CFR	Code of Federal Regulations
CGRP	calcitonin gene-related peptide
C min	minimum plasma drug concentration
C-SSRS	Columbia-Suicide Severity Rating Scale
CYP	cytochrome P450
CYP3A4	cytochrome P450 3A4
DSMB	Data and Safety Monitoring Board
ECG	electrocardiogram
eCRF	electronic case report form
eDiary	electronic diary
EM	episodic migraine
EMA	European Medicines Agency
ET	early termination
eTablet	electronic tablet
EU	European Union
FDA	Food and Drug Administration
GBD2010	Global Burden of Disease Survey 2010
GCP	Good Clinical Practices
GI	gastrointestinal
GLP	Good Laboratory Practice
HIPAA	Health Insurance Portability and Accountability Act
HIV	human immunodeficiency virus
HSG	hysterosalpingogram
IB	investigators brochure
ICF	informed consent form
ICH	International Conference on Harmonisation
ICHD-3	International Classification of Headache Disorders criteria, 3 rd edition
IEC	Independent Ethics Committee

Term/ Abbreviation	Definition
IgG	immunoglobulin G
IgM	immunoglobulin M
IHS	International Headache Society
INR	international normalized ratio
IRB	Institutional Review Board
ITT	intent-to-treat
IUD	intrauterine device
IUS	intrauterine system
IV	intravenous
IWRS	interactive web response system
MAR	missing-at-random
MedDRA	Medical Dictionary for Regulatory Activities
MI	multiple imputation
mITT	modified intent-to-treat
MMRM	mixed-effects model for repeated measures
MNAR	missing-not-at-random
MSQ v2.1	Migraine Specific Quality of Life Questionnaire, version 2.1
NA	not applicable
NSAID	nonsteroidal anti-inflammatory drug
OATP1B1	organic-anion-transporting polypeptide 1B1
PD	pharmacodynamic
PK	pharmacokinetic
PMM	pattern-mixture model
PRO	Patient-Reported Outcome
QTcF	QT interval corrected for heart rate using the Fridericia formula
SAE	serious adverse event
SAP	statistical analysis plan
SNRI	serotonin–norepinephrine reuptake inhibitors
SOC	system organ class
SSRI	selective serotonin reuptake inhibitors
SUSAR	suspected unexpected serious adverse reaction
TEAE	treatment-emergent adverse event
ULN	upper limit of normal
VAS	visual analogue scale
VCT	Verified Clinical Trials

QTcB	QT interval corrected for heart rate using the Bazett formula $(QTcB = QT/(RR)\frac{1}{2})$
QTcF	QT interval corrected for heart rate using the Fridericia formula (QTcF = QT/(RR) $\frac{1}{3}$)
SAE	serious adverse event
SAP	statistical analysis plan
SI	Le Système International d'Unités (International System of Units)
SOC	standard of care
TBL	total bilirubin
TEAE	treatment-emergent adverse event
WHO	World Health Organization
_	

4 Introduction

This statistical analysis plan (SAP) details comprehensive, technical specifications of the statistical analyses of the efficacy and safety data outlined and/or specified in the protocol amendment #3 (dated 14 May 2020) of Study 3101-301-002. Specifications of tables, figures, and data listings are contained in a separate document.

This study is a multicenter, randomized, double-blind, placebo-controlled, parallel-group study conducted in the United States and will enroll approximately 872 participants from approximately 110 sites. Participants will be randomized to one of four treatment arms (placebo, atogepant 10 mg, atogepant 30 mg, and atogepant 60 mg) in a 1:1:1:1 ratio. Approximately 70% of randomized participants will have taken at least 1 prior migraine prevention medication with proven efficacy. Randomization will be stratified based on prior exposure (yes/no) to a migraine prevention medication with proven efficacy.

[figure not shown]
The study will consist of a 4-week screening and baseline period, a 12-week double-blind treatment period, and a follow up period of 4 additional weeks, for a total duration of 20 weeks. Participant participation will begin with a 4-week screening/baseline period. Participants who complete the 4-week screening/baseline period and meet all entry criteria will be randomized to the double-blind treatment period of the study at Visit 2 (Randomization Visit). The double-blind treatment period will last 12 weeks, with a subsequent follow-up period of 4 additional weeks. There will be 8 scheduled clinic visits: Visit 1 (Screening/Baseline), Visit 2 (Randomization), Visit 3 (Week 2), Visit 4 (Week 4), Visit 5 (Week 6), Visit 6 (Week 8), Visit 7/ET (Week 12), and Visit 8 (Follow-up). The Visit 8 (Follow-up) must be completed for all participants who take at least one dose of study intervention, except for participants rolling over into Study 3101-309-002 (long-term safety extension study). For these participants Visit 8 is not required, as the Follow-up Visit will be performed in the long-term safety study. For participants who screen fail for the long-term safety, the Follow-up Visit must be completed.

Per study design (Protocol Sections 8.4.3.2 and 8.8), eDiary data will be collected for participants who early terminated from the double-blind treatment period during the 4 weeks between V7 (Early termination visit) and V8 (Follow-up Visit).

After the last patient first visit on January 31,2020, COVID-19 pandemic emerged. The Section 0 is added to specify analyses for evaluating the impact of COVID-19.

Figure 4-1 Study Design

Allergan		SAP 3101-301-002 AGN-241689

[figure not shown]

5 Study Objectives

- To evaluate the safety and tolerability of atogepant 10 mg, atogepant 30 mg and 60 mg for the prevention of migraine in participants with EM.
- To prospectively test for superiority of atogepant 10 mg, atogepant 30 mg and 60 mg versus placebo for the prevention of migraine in participants with EM.

6 Analysis Populations

The analysis populations will consist of participants as defined below.

The Intent-to-Treat (ITT) Population includes all randomized participants.

The Safety Population includes all participants who received at least 1 dose of study intervention. All safety analyses will be performed using the Safety Population and based on the treatment actually received, regardless of assigned treatment according to the planned randomization. Participants will be summarized according to the study treatment received for the majority of treatment period.

The Modified Intent-to-Treat (mITT) Population includes all randomized participants who received at least 1 dose of study intervention, had an evaluable baseline period of eDiary data and had at least 1 evaluable post-baseline 4-week period (Weeks 1 to 4, 5 to 8, and 9 to 12) of eDiary data during the double-blind treatment period. All efficacy analyses described in Sections 10.2 - 10.4 will be performed using the mITT population and based on the randomization assignment, regardless of the actual treatment received. All efficacy analyses will be conducted using mITT population unless specified otherwise.

The analysis population for Off-treatment Hypothetical Estimand includes all randomized participants who received at least 1 dose of study treatment, had an evaluable baseline period of eDiary data and had at least 1 evaluable post-baseline 4-week period (Weeks 1 to 4, 5 to 8, 9 to 12) of eDiary data during the DB treatment period and follow-up period, regardless of whether on study treatment or off study treatment.

7 Participant Disposition

The number of participants in the ITT, Safety, and mITT Populations will be summarized by treatment group; the number of participants screened will be summarized for overall only. The number of participants in the ITT Population will also be summarized by treatment group for the

SAP 3101-301-002 AGN-241689

following factors: 1) Randomization stratification factor (prior exposure [yes/no] to a migraine prevention medication with proven efficacy) from IWRS; 2) Prior exposure to migraine prevention medication with proven efficacy based on prior medication collected from eCRF, which will be termed as "actual strata" in the SAP. The list of participants with incorrect randomization stratum will be provided.

[figure not shown]
Screen-failure participants (i.e., participants screened but not randomized) and the associated reasons for failure to randomize will be tabulated overall for the all screened participants. The number and percentage of participants who enter the double-blind treatment period, complete the double-blind treatment period and of participants who prematurely discontinue during the same period will be presented for each treatment group and pooled across treatment groups for all randomized participants. The reasons for premature discontinuation from the double-blind treatment period as recorded on the termination pages of the electronic case report forms will be summarized (number and percentage) by treatment group. The percentage is relevant to the total number of randomized participants. Similar disposition information to the double-blind treatment period will be presented for the follow-up period. All randomized participants who prematurely discontinue during the double-blind treatment period or the follow-up period will be listed by discontinuation reason. The number of participants who signed informed consent for Safety Extension Study 3101-309-002 will be provided.

8 Demographic and Other Baseline Characteristics

Demographic parameters (age; age group [< 20, 20-29, 30-39, 40-49, 50-59, 60-69, and \ge 70]; race; race group [white, all other races]; ethnicity; sex), baseline characteristics (weight; height; and body mass index, calculated as weight [kg]/(height [m])² will be summarized descriptively by treatment group for the Safety and mITT Populations, and Off-treatment Hypothetical Estimand Population. Continuous variables will be summarized by number of participants and mean, SD, median, first quartile (Q1), third quartile (Q3), minimum, and maximum values. Categorical variables will be summarized by number and percentage of participants.

Abnormalities in participants' medical and surgical history will be coded using the Medical Dictionary for Regulatory Activities, version 22.0 or newer. The number and percentage of participants with abnormalities in medical and surgical histories in each system organ class and preferred term will be summarized by treatment group for the Safety Population.

Migraine history, including diagnosis, duration of disorder, use of migraine prevention medication in the past, average number of migraine or headache days per month in the last 3

months, acute medications taken to treat migraine headaches, and advice on lifestyle alterations will be reported in total and by treatment group for the Safety Population.

Prior medication is defined as any medication taken before the first dose of double-blind study treatment. Concomitant medication is defined as any medication taken on or after the date of the first dose of the double-blind study treatment.

Prior medication use will be summarized by the number and proportion of participants in each treatment group receiving each medication within each therapeutic class for the Safety Population. Concomitant medication use will be summarized by the number and percentage of participants in each treatment group receiving each medication within each therapeutic class for the double-blind treatment period and follow-up period for the Safety Population. If a participant took a specific medication multiple times or took multiple medications within a specific therapeutic class, that participant would be counted only once for the coded drug name or therapeutic class. Any prior and concomitant medications will be included in listings.

The World Health Organization (WHO) Drug Dictionary Enhanced, March 2017 or newer, will be used to classify prior and concomitant medications by therapeutic class and drug name.

Protocol deviations will be defined in Protocol Deviation Requirement Specification (PDRS), including significant classification. The number and percentage of participants with significant protocol deviations will be summarized by treatment group for all categories specified in PDRS for all randomized participants.

Baseline efficacy parameters (monthly migraine days, monthly headache days, monthly acute medication use days, Migraine Specific Quality of Life Questionnaire [MSQ] v2.1 Role Function Restrictive domain score, Performance of Daily Activities domain score of the AIM-D, and Physical Impairment domain score of the AIM-D) will be summarized by treatment group for mITT Population and Off-treatment Hypothetical Estimand Population.

9 Extent of Exposure and Treatment Compliance

9.1 Extent of Exposure

Exposure to double-blind study treatment for the Safety Population during the treatment period will be summarized for treatment duration, calculated as the number of days from the date of the first dose of double-blind study treatment taken to the date of the last dose taken, inclusive. The number and percentage of participants with each treatment duration of ≥ 1 day, ≥ 7 days, ≥ 14 days, ≥ 21 days, ≥ 28 days, ≥ 35 days, ≥ 42 days, ≥ 49 days, ≥ 56 days, ≥ 63 days, ≥ 70 days, ≥ 70 days, ≥ 84 days will be summarized by treatment group respectively. Descriptive

Allergan SAP 3101-301-002 AGN-241689

statistics (number of participants, mean, SD, median, Q1, Q3, minimum, and maximum) will also be summarized by treatment group.

Participant-years, defined as exposure to the study treatment in years, will be summarized by treatment group for the Safety Population.

9.2 Measurement of Treatment Compliance

Dosing compliance for a specified period is defined as the total number of double-blind study medications actually taken by a participant during that period divided by the number of double-blind study medications that were expected to be taken during the same period multiplied by 100. The total number of tablets actually taken during a specific period will be calculated from the study medication record. The prescribed number of tablets during a specific period will be calculated as following: 3 tablets/day \times the number of days during the period. Descriptive statistics for double-blind study medication dosing compliance together with the compliance categories (< 80%, 80% - 120%, > 120%) will be summarized by treatment group for each period between 2 consecutive visits, as well as for the period from the first dose of the double-blind study interventions actually taken to the last dose of double-blind study intervention actually taken for the Safety Population.

10 Efficacy Analyses

10.1 Efficacy and Health Outcome Measures

10.1.1 Efficacy Measures

A migraine day is defined as any calendar day on which a headache occurs which meets criteria A, B, and C OR meets criteria D and E, as listed below, as per participant eDiary. Calendar days begin at midnight and last until 11:59 PM (23:59).

- A. Headache has at least two of the following four characteristics:
 - i. Unilateral location
 - ii. Pulsating quality
 - iii. Moderate or severe pain intensity
 - iv. Aggravated by or causing avoidance of routine physical activity (eg, walking or climbing stairs)
- B. At least one of the following:
 - i. Nausea and/or vomiting
 - ii. Photophobia and phonophobia

SAP 3101-301-002 AGN-241689

- iii. Typical aura (i.e., visual, sensory, or speech/language) accompanying or within 60 minutes before headache begins
- C. Duration of headache lasting 2 hours or longer on a calendar day unless an acute, migraine-specific medication (i.e., triptan or ergot derivative) was used after the start of the headache, in which case no minimum duration will be specified

OR

- D. Any headache which fulfills one criterion from (1) and at least one criterion from (2) **OR** fulfills at least two criteria from (1) and no criteria from (2).
 - 1) Headache characteristics:
 - i. Unilateral location
 - ii. Pulsating quality
 - iii. Moderate or severe pain intensity
 - iv. Aggravated by or causing avoidance of routine physical activity (eg, walking or climbing stairs)
 - 2) Symptoms:
 - i. Nausea and/or vomiting
 - ii. Photophobia and phonophobia
 - iii. Typical aura (i.e., visual, sensory, or speech/language) accompanying or within 60 minutes before headache begins
- E. Duration of headache lasting 2 hours or longer on a calendar day unless an acute, migraine-specific medication (i.e., triptan or ergot derivative) was used after the start of the headache, in which case no minimum duration will be specified.

A headache day is defined as any calendar day on which headache pain lasting 2 hours or longer occurs unless an acute headache medication (eg, ibuprofen, triptan) was used after the start of the headache, in which case no minimum duration will be specified. Note that antiemetics will not be counted as an acute headache medication for headache day identification. Calendar days begin at midnight and last until 11:59 PM (23:59).

An acute medication use day is defined as any day on which a participant reports, per eDiary, the intake of allowed medication(s) to treat an acute migraine. The allowed medications include the following categories of drugs: triptans, ergots, opioids, analgesics (including acetaminophen), NSAIDs (including aspirin), and antiemetics.

SAP 3101-301-002 AGN-241689

A triptan use day is defined as any day on which a participant reports intake of a triptan to treat a migraine per participant diary.

Headache day pain intensity is defined as the worst pain intensity on any headache day where headache pain intensity will be subjectively rated by the patient on a scale from mild to severe:

- Mild pain (=1)
- Moderate pain (=2)
- Severe pain (=3)

If participants experience no headache in a day, then the corresponding pain intensity of that day will be set as missing.

10.1.2 Health Outcome Measures

The AIM-D is an 11-item daily diary measure that assesses the impact of migraine and is comprised of two domains that evaluate performance of daily activities (7 items) and physical impairment (4 items). Participants are asked to rate the level of difficulty experienced in the past 24 hours with performance of daily activities (i.e., difficulty with household chores, errands, leisure activities at home, leisure or social activities outside the home, strenuous physical activities, concentrating, and thinking clearly) and physical impairment (i.e., difficulty walking, moving body, bending forward, moving head) using a 6-point rating scale ranging from "Not difficult at all," "A little difficult," "Somewhat difficult," "Very difficult," "Extremely difficult," and "I could not do it at all." Three items include a response of "I did not...," for example, "I did not have errands planned." The AIM-D was developed as an electronic daily diary with the same set of questions administered in headache and non-headache versions. The Headache version is administered on days when a participant reports a headache and the Non-Headache version is administered on days when a participant does not report having a headache. The AIM-D instructs participants to answer each question based on the level of difficulty experienced in the past 24 hours for both versions, with "during your headache" indicated for the AIM-D Headache version. In addition to the two domain scores, a total score using all 11 items can also be calculated. Each raw daily domain score, as well as the raw daily total score, are transformed to a 0-100 scale, with higher scores indicating greater impact of migraine (i.e., higher disease burden).

[figure not shown]
Two items based on a 24-hour recall will be administered daily using Headache and Non-headache versions as additional health outcome measures and for evaluation of the AIM-D. The first item will be used to assess activity level within the past 24 hours with a 5-level response scale ranging from "No activity – Spent all day lying down" to "Exercised – Brisk

Allergan SAP 3101-301-002 AGN-241689

walk, running, jogging, biking or other activity for 30 or more minutes." The second item will be used to evaluate activity limitation with a 5-level response scale ranging from "Not at all limited – I could do everything" to "Extremely limited".

The MSQ v2.1 is a 14-item questionnaire designed to measure health-related quality-of-life impairments attributed to migraine in the past 4 weeks. It is divided into three domains: Role Function Restrictive assesses how migraines limit one's daily social and work-related activities; Role Function Preventive assesses how migraines prevent these activities; and the Emotional Function domain assesses the emotions associated with migraines. Participants respond to items using a 6-point scale ranging from "none of the time" to "all of the time." Raw dimension scores are computed as a sum of item responses and rescaled to a 0 to 100 scale, where higher scores indicate better quality of life.

10.2 Primary Efficacy Endpoints

The primary efficacy endpoint is the change from baseline in mean monthly migraine days across the 12-week treatment period. The primary null hypothesis is that atogepant treatment doses (atogepant 10 mg, atogepant 30 mg, and atogepant 60 mg once a day) are each equally effective to placebo in mean change from baseline in mean monthly migraine days across the 12week treatment period. The alternative hypothesis is that at least 1 of the 3 doses of atogepant has a different effect than placebo. Baseline is defined as the number of migraine days during the last 28 days prior to the randomization date.

10.2.1 Primary Analysis

The endpoint will be analyzed using a mixed model for repeated measures (MMRM). The response variable is the change from baseline to each postbaseline month in monthly migraine days. The model will include treatment group, visit (derived as month), prior exposure (yes/no) to a migraine prevention medication with proven efficacy, and treatment group by visit interaction as categorical fixed effects. It will also include the baseline score and baseline-byvisit interaction as covariates. The stratum "prior exposure (Yes/No)" will use the actual stratification factor from prior medication collected by eCRF. The analysis will be performed based on evaluable postbaseline data using only the observed cases without missing data imputation. Only data collected during the double-blind period will be included in the analysis. Participants are always analyzed based on the treatment group assigned by randomization.

Restricted maximum likelihood method will be used. The within-patient correlation will be modeled using the unstructured covariance matrix. If the model does not converge, then the Toeplitz covariance structure will be used. if the model with the Toeplitz covariance structure does not converge, then the compound symmetry covariance structure will be used. The Kenward-Roger approximation will be used to estimate denominator degrees of freedom. Contrasts will be constructed to obtain the average treatment effects across the 12-week treatment period to compare each atogepant treatment group versus the placebo group. Each

Allergan SAP 31	01-301-002 AGN-241689
treatment effect and treatment comparisons will be estimated by the LS	Means and their
differences in LS Means, along with their SE and 95% confidence inter	vals, and the p-value
corresponding to the between-treatment group difference. The sample S	AS code is given as
follows	

[figure not shown]

The impact of dropouts on the primary efficacy measure will be explored graphically by plotting the response profiles by the dropout reason. Plot of mean change from baseline in the number of migraine days versus visit (month) based on the observed cases will be provided in each treatment group by major reason of early termination, such as, adverse events, lack of efficacy, withdrawal of consent, lost to follow-up, etc. Similar plot for completers in each treatment group will be provided as a reference.

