#### 7.3.1 Primary Efficacy Analyses

The primary efficacy endpoint is the change from baseline in mean monthly migraine days across the 12-week treatment period. The primary null hypothesis is that atogepant treatment doses (atogepant 10 mg, atogepant 30 mg, and atogepant 60 mg once a day) are each equally effective to placebo in mean change from baseline in mean monthly migraine days across the 12-week treatment period. The alternative hypothesis is that at least 1 of the 3 doses of atogepant has a different effect than placebo.

The primary comparison between treatment groups will be done by a mixed-effects model for repeated measures (MMRM) of the change from baseline. The statistical model will include treatment group, visit, prior exposure (yes/no) to a migraine prevention medication with proven efficacy, and treatment group by visit interaction as categorical fixed effects. It will also include the baseline score and baseline-by-visit interaction as covariates. An unstructured covariance matrix will be used to model the covariance of within-participant repeated measurements. The Kenward-Roger approximation ([Kenward 1997](#)) will be used to estimate the denominator degrees of freedom. The analysis will be performed based on all postbaseline values using only the observed cases without imputation of missing values. Pairwise contrasts in the MMRM model will be used to make the pairwise comparisons of each atogepant dose to placebo.

Only data collected during the double-blind period will be included in the analysis. Participants are always analyzed based on the treatment group assigned by randomization.

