10.3 Secondary Efficacy Endpoints

The secondary efficacy endpoints for the United States and the EU are as follows:

- Change from baseline in mean monthly headache days across the 12-week treatment period.
- Change from baseline in mean monthly acute medication use days across the 12-week treatment period.
- \geq 50% reduction in 3-month average of monthly migraine days
- Change from baseline in MSQ v2.1 Role Function Restrictive domain score at Week 12.
- Change from baseline in mean monthly Performance of Daily Activities domain score of the AIM-D across the 12-week treatment period.
- Change from baseline in mean monthly Physical Impairment domain score of the AIM -D across the 12-week treatment period.

The secondary endpoints for headache days, acute medication use days, Performance of Daily Activities domain score of the AIM-D, and Physical Impairment domain score of the AIM-D will be analyzed in the same manner as that used to analyze the primary endpoint. For MSO v2.1 Role Function Restrictive domain score, the analysis will be performed similarly to the primary MMRM, with focus on the pairwise contrasts of each dose group to placebo at Week 12. Week

[figure not shown]
Allergan	
7 the gan	

SAP 3101-301-002 AGN-241689

16 (follow-up visit) data for MSQ v2.1 Role Function Restrictive domain score will not be included in MMRM analysis, and only summary statistics for Week 16 will be provided. The corresponding sample SAS code is given as follows

The 50% responder, defined as a participant with at least a 50% reduction from baseline in the 3-month average of monthly migraine days, will be assessed for each individual. A logistic regression model will be used to analyze the 50% responders across the 12-week treatment period. This model assumes a binary distribution for the response and uses a logit link. The analysis model will include treatment group, prior exposure (yes/no) to a migraine prevention medication with proven efficacy, and baseline monthly migraine days. The treatment difference in terms of odds ratio between each atogepant dose group and placebo will be estimated and tested from this model. The sample SAS is given as follows

[figure not shown]
Allergan		SAP 3101-301-002 AGN-241689

Allergan	SAP 3101-301-002 AGN-241689

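### If the unstructured model fails, the SAP's fallback covariance structures assume equal variance at every visit, which could misstate the standard error of the single-visit Week 12 MSQ test

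*SAP*

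**What the plan says.** Protocol 7.3.1 gives one covariance structure and no alternative: "An unstructured covariance matrix will be used to model the covariance of within-participant repeated measurements".

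SAP 10.2.1 starts from the same place ("The within-patient correlation will be modeled using the unstructured covariance matrix", fitted by REML) and adds a two-step rule. First, "If the model does not converge, then the Toeplitz covariance structure will be used". Then, "if the model with the Toeplitz covariance structure does not converge, then the compound symmetry covariance structure will be used". On inference it says "The Kenward-Roger approximation will be used to estimate denominator degrees of freedom". Neither fallback is named in its heterogeneous-variance form, and the readable text mentions no empirical (sandwich) variance.

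For the primary endpoint the tested quantity is an average over visits: "Contrasts will be constructed to obtain the average treatment effects across the 12-week treatment period".

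For MSQ Role Function-Restrictive, SAP 10.3 says "the analysis will be performed similarly to the primary MMRM, with focus on the pairwise contrasts of each dose group to placebo at Week 12". That is a contrast at one visit. SAP Table 18-1 lists this endpoint as Secondary 4, node S4, so it belongs to the confirmatory testing.

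The sample SAS code announced in SAP 10.2.1 and 10.3 is not shown in the public copy.

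**The concern.** Toeplitz and compound symmetry, as ordinarily defined, have a single variance parameter for all visits. They differ only in how correlation depends on the distance between visits. Kenward-Roger allows for the covariance parameters having been estimated. It does not allow for the covariance having the wrong shape.

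For a contrast averaged over all visits this matters little, because pooling the variances and covariances leaves the variance of the average almost unchanged. For a contrast at one visit, the model uses the pooled variance in place of the variance at that visit. If scores are more spread out at Week 12 than earlier, the standard error is too small and the test rejects too often. If they are less spread out, the standard error is too large and power is lost.

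At stake is the error rate of one test in the alpha-controlled sequence, and only where the fallback is actually used.

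**Working it through.** **Inputs from the documents.** 218 planned per arm; two-sided 0.0167 per dose comparison; primary difference -1.5 days with SD 3.5 (SAP 15). 910 randomized (SAP 18.1).

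**Assumptions, not in the documents.** Three MSQ visits in the model, the SD patterns and correlations below, and 0.0167 as the local level at S4. The readable SAP gives 0.0167 in its sample-size section; the graph that sets the level at each node is not shown.

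**The plan's own figure.** The SE of the primary difference is 3.5 × √(2/218) = 0.335, and 1.5/0.335 = 4.474. The critical value is 2.393. Power is Φ(4.474 − 2.393) = 98.1%, against the stated 98%. The documents give no SD, SE or power for MSQ, so nothing there can be reproduced.

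**Week 12 contrast.** With complete data, and with treatment and baseline effects free at each visit, the Week 12 SE depends only on the variance that the model assigns to Week 12. Under compound symmetry this is the mean of the visit variances. A fitted Toeplitz gives nearly the same value. So:

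- SE ratio r = √(mean of visit variances) / Week 12 SD
- actual size = 2 × [1 − Φ(2.393 × r)]

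For SD ratios 1:1.1:1.2, the mean variance is (1 + 1.21 + 1.44)/3 = 1.2167, its root is 1.103, and r = 1.103/1.2 = 0.919. Then 2.393 × 0.919 = 2.200 and the size is 0.028.

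| Assumed SD ratios | r | Size of nominal 0.0167 test |
|---|---|---|
| 1:1:1 | 1.000 | 0.0167 |
| 1:1.05:1.1 | 0.955 | 0.022 |
| 1:1.1:1.2 | 0.919 | 0.028 |
| 1:1.15:1.3 | 0.890 | 0.033 |
| 1.2:1.1:1.0 | 1.103 | 0.008 |

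**Twelve-week average.** Take SDs 1, 1.1, 1.2 and an adjacent-visit correlation of 0.7. If the first-to-third correlation is 0.6, the true variance of the average is [3.65 + 2 × (0.77 + 0.924 + 0.72)]/9 = 0.9420. Compound symmetry reproduces it exactly; the best-fitting Toeplitz gives 0.9428. If that correlation is 0.49, the figures are 0.9127 and 0.9144. The SE ratio is below 1.001 in both. Over a wider set of patterns, up to SDs of 16/20/24 or the reverse, it was at most 1.004.

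**Simulation with dropout.** 218 per arm, 12% completely random monotone dropout, REML fits, normal critical value at 0.0167:

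| SDs | Model | Runs | Mean model SE | Empirical SD | Rejection rate |
|---|---|---|---|---|---|
| 18/20/22 | compound symmetry | 1000 | 1.98 | 2.21 | 0.037 |
| 18/20/22 | Toeplitz | 1000 | 1.99 | 2.19 | 0.029 |
| 22/20/18 | compound symmetry | 600 | 2.01 | 1.80 | 0.008 |
| 22/20/18 | unstructured | 600 | 1.79 | 1.84 | 0.025 |
| 20/20/20 | compound symmetry | 600 | 1.98 | 1.95 | 0.013 |

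The complete-data formula gives 0.029 for 18/20/22 and 0.008 for 22/20/18. At a true rate of 0.0167 the Monte Carlo standard error is about 0.004 with 1000 runs and 0.005 with 600. The unstructured and equal-SD rates therefore fit the nominal level, and the direction of the other results agrees with the formula. Heterogeneous structures were not simulated.

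**The case against.** The best defence is that the rule will almost certainly never be used. With three visits an unstructured matrix has 6 parameters, and 910 participants were randomized. The sizes in the table are conditional on failure. If failure had a probability of 1% (an assumption) and were unrelated to the test result, the overall size under the 1:1.15:1.3 pattern would be 0.01 × 0.033 + 0.99 × 0.0167 = 0.0169. This stands, and it is why the point is small.

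Three further objections also stand in part. The SAS code is not shown, so a heterogeneous or empirical option in it can be neither confirmed nor excluded. SAP 10.3 treats MSQ as similar to the primary model and announces separate code, so the carry-over of the fallback is the natural reading but is not stated. And with three visits heterogeneous Toeplitz has 5 parameters against 6 for unstructured, so it may give little relief when the unstructured fit fails; heterogeneous compound symmetry, with 4, gives more.

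A reader might also infer that SAP 19, which reports no changes from the protocol, is wrong because the protocol has no fallback. That is not well supported: a pre-specified non-convergence rule elaborates the protocol's analysis and leaves the planned model in place.

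**Conclusion.** The point holds in a limited form. The fallbacks as named can misstate the standard error of the Week 12 MSQ contrast, provided that the unstructured fit fails, the rule applies to MSQ, and the Week 12 variance differs from the average over visits. Under the assumed SD patterns the size of a nominal 0.0167 test runs from about 0.008 to 0.033.

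Two stronger readings are tempting. One is that the fallback gives a wrong standard error, or inflates type I error, as a matter of course. The documents do not support it: they contain no MSQ variances by visit, equal variances produce no error, and falling variances make the test conservative. The other is that the primary analysis is compromised. It is not, because the primary and the other MMRM endpoints averaged over 12 weeks keep essentially the right standard error even under the fallback.

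With incomplete data a wrong covariance could also affect how the likelihood adjusts for data missing at random. That effect was not quantified and the conclusion does not rest on it.

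**What to change.** In SAP 10.2.1, name heterogeneous Toeplitz and then heterogeneous compound symmetry as the fallbacks, ahead of any homogeneous structure. In SAP 10.3, state that the same sequence applies to the MSQ model. If the SAS code already does this, the prose should say so.

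If a homogeneous structure is ever needed as a last resort, a sandwich variance with a compatible degrees-of-freedom method is a reasonable alternative to Kenward-Roger. It need not be mandatory, since the heterogeneous structures alone deal with the problem described here.

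The cost is one or two sentences and a programming option. With three visits each heterogeneous structure has two more parameters than its homogeneous counterpart (5 against 3 for Toeplitz, 4 against 2 for compound symmetry). The sample size and the planned unstructured model do not change.
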